5.7.2 Intra-Individual Dose Escalation of Azacitidine Beyond Starting Dose

In patients treated with twice a week azacitidine we have measured the plasma activity of the azacitidine inactivating enzyme cytidine deaminase (CDA) by an HPLC method that quantifies deamination of added cytidine. Responders had significantly lower plasma CDA activities than non-responders suggesting that destruction of azacitidine precluded response (submitted to ASH 2012). Patients who do not achieve a reduction of monoclonal proteins to MR range after the first cycle or to PR range after the second cycle and who have tolerated the previous cycle at their full starting dose of azacitidine twice a week without dose reduction or delay due to toxicities may therefore be treated with 75mg/ m^2 azacitidine in the next cycle and if an entire cycle at this dose level is

tolerated without the need for dose reduction or delay due to toxicities but monoclonal proteins are still not in MR range after one cycle or PR range after two cycles at this azacitidine dose, the dose of azacitidine may further be increased to 100mg/m². There will be no intra-individual dose escalation of azacitidine beyond 100mg/m².

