5.1 Overall Design

This phase I/II trial will use a classical 3x3 design to determine the highest tolerated low dose (HTLD) for patients with GFR $\geq 60 \text{ ml/min}$ (Cockroft-Gault) and a modified 3x3 design to identify the highest tolerated low dose for patients with GFR 30-59 ml/min (HTLD-CKD) with additional enrollment of 10 patients at the highest tolerated low doses (HTLD / HTLD-CKD) of azacitidine.

Dose levels are outlined under 5.6.2.3.

Dose limiting toxicity (DLT) is defined as one of the following drug-related toxicities occurring during the first 28-day cycle (if a DLT is attributed to progressive disease, it will not be counted as a DLT):

- Any CTCAE v.4.0 grade ≥ 3 non hematologic toxicity (including febrile neutropenia)
 - For nausea, vomiting, or diarrhea, subjects must have a Grade 3 or 4 event that persists at this level despite the use of optimal symptomatic treatment, in order for these events to be considered a DLT

- Grade 4 transaminitis (serum transaminase $> 20 \times$ upper limit of normal [ULN]) is a DLT, while Grade 3 transaminitis (serum transaminase $> 5 \times$ and $\leq 20 \times$ ULN) must be present for ≥ 7 days to be considered a DLT
- Grade 3 or 4 venous thromboembolic events are not considered to be DLTs as long as anticoagulant therapy can be administered (see Section 6.5.3 and 6.6.2)
- Grade 3 or 4 hypokalemia, hypophosphatemia, hypomagnesemia or hyponatremia that responds to electrolyte supplementation within 7 days would not qualify as a DLT.
- CTCAE v.4.0 grade ≥ 4 neutropenia or thrombocytopenia that does not resolve to grade ≤ 3 within seven days of holding azacitidine and lenalidomide. While platelet transfusions are allowed at the discretion of the treating physician to maintain 100% dose level, any grade ≥ 4 thrombocytopenia that is followed by platelet transfusion prior to resolution to grade ≤ 3 will be counted as DLT.

Dose escalation for patients with GFR $\geq 60\text{ml/min}$:

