5.7.1 Dose Modification Steps and Dose Re-Escalation Guidelines

5.7.1.1 Dose Modification Steps

Table 1: Lenalidomide dose modification steps for all toxicities listed in Table 5 EXCEPT for renal impairment or toxicities in the presence of renal impairment*

Current Lenalidomide Dose	One Level Dose Reduction
25 mg daily on Days 1-21 every 28 days	20 mg daily on Days 1-21 every 28 days
20 mg daily on Days 1-21 every 28 days	15 mg daily on Days 1-21 every 28 days
15 mg daily on Days 1-21 every 28 days	10 mg daily on Days 1-21 every 28 days
10 mg daily on Days 1-21 every 28 days	5 mg daily on Days 1-21 every 28 days
5 mg daily on Days 1-21 every 28 days	Discontinue lenalidomide

* Renal impairment is defined as calculated creatinine clearance \geq 30mL/min but $<$ 60mL/min (see Table 2 below for lenalidomide dosing)

Table 2: Lenalidomide dose modification steps for renal impairment (see Table 5) and for other toxicities which occur after dose reduction for renal impairment*

Current Lenalidomide Dose	One Level Dose Reduction
25 mg daily on Days 1-21 every 28 days	10 mg daily on Days 1-21 every 28 days
10 mg daily on Days 1-21 every 28 days	15 mg every 48 hours during Days 1-21 every 28 days
15 mg every 48 hours during Days 1-21 every 28 days	5 mg daily on Days 1-21 every 28 days
5 mg daily on Days 1-21 every 28 days	Discontinue lenalidomide

* Renal impairment is defined as calculated creatinine clearance $\geq 30\text{mL/min}$ but $< 60\text{mL/min}$

Table 3: Azacitidine Dose Adjustment Steps

Dose Level +2	100 mg/ m^2 SC twice a week (only for patients on twice a week azacitidine who tolerated azacitidine 75mg/ m^2 SC twice a week but did not respond, see under 5.7.1.2)
Dose Level +1	75 mg/ m^2 SC twice a week (only for patients on twice a week azacitidine who tolerated their full azacitidine starting dose but did not respond, see under 5.7.1.2)
Dose Level 0	Starting azacitidine dose (differs depending on cohort during phase I part, see 5.6.2.3)
Dose Level -1	Reduce dose by 50%, maintain frequency of administration
Dose Level -2	Discontinue azacitidine

Table 4: Dexamethasone Dose Reduction Step

Dose Level – 1	Reduce each dexamethasone dose by 50%
Dose Level – 2	Discontinue dexamethasone

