5.7.4 Instructions for Initiation of a New Cycle

A new course of treatment may begin on the scheduled Day 1 of a new cycle if:

- The ANC is $\geq 1000/\text{mm}^3$ (G-CSF is allowed to achieve this threshold)
- The platelet count is $\geq 50,000/\text{mm}^3$ (During the first 4 cycles platelet transfusions are allowed to achieve this threshold)
- Any new drug-related neuropathy or rash other than injection site reaction that may have occurred has resolved to \leq grade 1 severity;
- Any bicarbonate decrease below 20mEq/L that may have occurred has resolved to baseline.
- Calculated creatinine clearance $\geq 30\text{ml}/\text{min}$ (by Cockroft-Gault), after 12 cycles on therapy, determining the creatinine clearance every 2 months will suffice
- Any other drug-related adverse events that may have occurred have resolved to \leq grade 2 severity. Physician discretion may be used in initiating the next cycle of treatment if the only toxicities that have not resolved to \leq grade 2 severity are dexamethasone-related toxicities.

If these conditions are not met on Day 1 of a new cycle, the subject will be evaluated weekly and a new cycle of treatment will not be initiated until the toxicity has resolved as described above. If criteria to initiate a new cycle are not met by 21 days after the planned start of a new cycle patients go off study. If a lenalidomide or azacitidine dose reduction was taken during the previous cycle, and the cycle was completed without requiring further dose modification, then the next cycle will start at the same reduced dose. **If lenalidomide and / or azacitidine dosing was omitted for the remainder of the previous cycle or if the new cycle is delayed due to toxicity newly encountered on the scheduled Day 1**, then the new cycle will be started with a one-level dose reduction of lenalidomide and/or azacitidine as appropriate. Dose reductions should generally be taken one drug at a time based on attribution of toxicity to one of the drugs unless otherwise indicated in Section 5.7.3.

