10.2 Datasets to be Analyzed

10.2.1 Dose Limiting Toxicity

Dose limiting toxicity is defined as any one of the following drug-related toxicities occurring during the first 28-day cycle (if a DLT is attributed to progressive disease, it will not be counted as a DLT):

- Any CTCAE v.4.0 grade ≥ 3 non hematologic toxicity (including febrile neutropenia)
 - For nausea, vomiting, or diarrhea, subjects must have a Grade 3 or 4 event that persists at this level despite the use of optimal symptomatic treatment, in order for these events to be considered a DLT
 - Grade 4 transaminitis (serum transaminase $> 20 \times$ upper limit of normal [ULN]) is a DLT, while Grade 3 transaminitis (serum transaminase $> 5 \times$ and $\leq 20 \times$ ULN) must be present for ≥ 7 days to be considered a DLT
 - Grade 3 or 4 venous thromboembolic events are not considered to be DLTs as long as anticoagulant therapy can be administered (see Section 6.5.3 and 6.6.2)

- Grade 3 or 4 hypokalemia, hypophosphatemia, hypomagnesemia or hyponatremia that responds to electrolyte supplementation within 7 days would not qualify as a DLT.
- CTCAE v.4.0 grade ≥ 4 neutropenia or thrombocytopenia that does not resolve to grade ≤ 3 within seven days of holding azacitidine and lenalidomide

Dose limiting toxicity will be assessed weekly during the first cycle. The highest tolerated low dose will be determined as described in Section 5.1.

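### No event count at 75 or 100 mg/m2 twice a week pauses azacitidine escalation for later patients; only patient-level gates apply

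*Combined protocol and SAP*

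**What the plan says.** Section 5.7.2 permits 75 mg/m2 in the next cycle for a patient short of minor response after cycle 1 or partial response after cycle 2, if the previous cycle at full starting dose needed no reduction or delay for toxicity. After a full tolerated cycle at 75 mg/m2 that still falls short on response, "the dose of azacitidine may further be increased to" 100 mg/m2. That is the ceiling: "There will be no intra-individual dose escalation of azacitidine beyond" 100 mg/m2. Table 3 in 5.7.1.1 restates the first gate: "only for patients on twice a week azacitidine who tolerated their full azacitidine starting dose but did not respond". The reason given is enzymatic inactivation of the drug: "Responders had significantly lower plasma CDA activities than non-responders suggesting that destruction of azacitidine precluded response".

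Other rules protect the individual. Table 5 holds or reduces drug. Under 5.7.4, when the restart criteria "are not met by 21 days after the planned start of a new cycle patients go off study".

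The rules that act across patients are tied to cycle 1. Section 10.2.1 reads "Dose limiting toxicity is defined as any one of the following drug-related toxicities occurring during the first 28-day cycle", and 5.1 and 6.2.1 use the same window. Section 5.1 alone adds that grade 4 or worse "thrombocytopenia that is followed by platelet transfusion prior to resolution to grade" 3 or lower counts as a DLT. Under 5.1 and 6.2.1, two DLTs end accrual at the level concerned; for GFR of at least 60 ml/min, 5.1 adds that patients already on treatment carry on under the protocol.

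**The concern.** The synopsis caps formal escalation at 50 mg/m2 twice a week, and the rationale in 3.3 regards nucleoside-analogue toxicity at 75 mg/m2 as close to certain. Yet the two-event rule that binds the PI at the lower doses does not extend to 75 and 100 mg/m2, which are 1.5 and 2 times that cap. If the first patients taken to a step have severe toxicity, the plan as written still lets the next eligible patient step up.

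The rules can also produce an inconsistent result. Two DLTs may close 40 or 50 mg/m2 as a starting level, while patients who started lower remain eligible to go directly to 75 mg/m2.

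**Working it through.** **1. Timing.** The DLT window is cycle 1. The earliest cycle at 75 mg/m2 is cycle 2 and at 100 mg/m2 cycle 3. No event at either step can be a DLT.

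**2. Reach of the two-DLT rule.** It closes accrual at the levels listed in 5.6.2.3, which end at 50 mg/m2 twice a week. Neither step is such a level.

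**3. Closed level, open step.** If two DLTs close 50 mg/m2 in either GFR group, patients who started at 40 may still go to 75. If two DLTs close CKD 1 (40 mg/m2), later patients start at 30 and may go directly to 75, which is 75/30 = 2.5 times their starting dose.

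**4. Exposure per 28 days, at 8 doses.** 8 x 50 = 400, 8 x 75 = 600 and 8 x 100 = 800 mg/m2. The approved MDS schedule cited in 3.3 gives 7 x 75 = 525 mg/m2, so the steps are 600/525 = 1.14 and 800/525 = 1.52 times that total. The MDS combination cited there gave 5 x 75 = 375 or 10 x 50 = 500 mg/m2 with lenalidomide 5-10 mg.

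**5. What the plan quantifies.** Its maximum enrolment of 44 reproduces: 18 already started + 4 to complete dose level 5 + 12 in the CKD levels + 10 in the extension = 44. It gives neither the number expected to be escalated nor an event rate at the steps. Both are assumed below.

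**6. Performance of a two-event rule.** Let X be the number of patients with an event among n escalated, binomial with true rate p.

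- P(pause) = 1 - (1-p)^n - np(1-p)^(n-1).
- Events averted, if outcomes become known one at a time and no one is escalated after the second event: np - 2 + 2P(X=0) + P(X=1).

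Example, n = 6 and p = 0.40: P(X=0) = 0.0467 and P(X=1) = 0.1866. P(pause) = 1 - 0.0467 - 0.1866 = 0.767. Averted = 2.4 - 2 + 0.0933 + 0.1866 = 0.680.

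| n escalated | P(pause), 10% | P(pause), 20% | P(pause), 40% | Averted, 20% | Averted, 40% |
|---|---|---|---|---|---|
| 3 | 0.03 | 0.10 | 0.35 | 0.008 | 0.06 |
| 4 | 0.05 | 0.18 | 0.52 | 0.03 | 0.20 |
| 6 | 0.11 | 0.34 | 0.77 | 0.12 | 0.68 |

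At a true rate of 15%, P(pause) is 0.06 with three patients and 0.22 with six.

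**7. Pooling.** With three patients in each GFR group and p = 0.40, separate two-event counts give 1 - (1 - 0.352)^2 = 0.58, against 0.77 pooled.

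**The case against.** The strongest reply is that oversight already exists and the gain is small. Grade 3 and 4 events are recorded with duration and action taken (6.2). Adverse events over 12 cycles are reported by dose level (10.2.2). SAEs go to the company within 24 hours, with site reports copied to the PI (6.3.1). A committee reviews trials twice a month (9.2), about twice per escalated cycle, and the study can be discontinued (11.5). This stands. A reader might infer that escalated patients are unmonitored, and the documents do not support that. What is absent is a threshold for these steps.

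The small gain also stands: with three or four escalated patients it is at most 0.20 events per step even at a 40% rate. The figures are a best case, because patients escalated at the same time would not benefit.

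A reader might further infer that these doses are shown to be unsafe and should be withdrawn. The documents do not show that. The expectation of toxicity at 75 mg/m2 rests on peak concentrations set against in-vitro thresholds. Section 3.3 describes the MDS combination as fairly well tolerated, 5.1.1.11 supports standard-dose azacitidine at GFR of 30 ml/min or above, and 3.2.1 cites weekly maximum tolerated doses up to 500 mg/m2, against 2 x 100 = 200 mg/m2 per week at the top step. None of these is the present three-drug regimen. Nor is the three-week break of the approved schedule a direct comparison: it follows seven daily doses totalling 525 mg/m2, whereas the steps give 150 or 200 mg/m2 per week in separated doses.

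Finally, the cycle-1 rule does not transfer perfectly. It serves to define a starting dose, escalated non-responders make attribution of cytopenias harder, and pooling mixes lenalidomide 25 mg and 10 mg. These are reasons to make the consequence a review rather than a permanent closure.

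**Conclusion.** The gap is established from the text alone: the gates in 5.7.2 look only at the individual, and no count of events at 75 or 100 mg/m2 triggers anything for later patients. It should be closed, because the plan followed as written carries no lesson from one escalated patient to the next at doses it expects to be more toxic.

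The benefit is modest: 0.01 to 0.12 events averted per step at a true 20% rate and 0.06 to 0.68 at 40%, for 3 to 6 escalated patients. Those figures rest on assumed event rates and numbers, independent patients, and outcomes known one at a time.

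It may be tempting to combine the pause probabilities for both steps as if the same six patients supplied each count independently. The 5.7.2 gate rules that out, since a patient with such an event at 75 mg/m2 would generally not qualify for 100 mg/m2. The per-step figures are the ones to use.

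**What to change.** In 5.7.2 and 6.2.1:

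- Apply the 5.1 DLT criteria, including the platelet-transfusion clause missing from 6.2.1 and 10.2.1, to each patient's first 28-day cycle at 75 mg/m2 and first at 100 mg/m2. Keep the same one-working-day notice to the PI.
- If two of the first up to six evaluable patients at a step have such an event, offer no further escalation to that step until the existing data safety and toxicity committee has reviewed it. Pool the count over starting doses and GFR groups, and show each GFR group as well.
- Let patients already tolerating the step continue under Table 5.

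The cost is weekly toxicity assessment in that cycle, which can use the existing injection visits. Weekly history and physical examination are now scheduled in cycle 1 only. Weekly CBC and metabolic panel already run through cycle 6, so they are extra only if a step is first taken later. An unnecessary pause at a step has probability about 11% at a true 10% rate and 22% at 15% if six are escalated, or 3% and 6% if three are. The rule also needs text on evaluability and pooling, so it is more than a one-line edit, but it requires no new committee.

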5.7.3 Dose Re-Escalation Guidelines

Dose Re-Escalation Upon Recovery from Hematologic Adverse Events

If the dose of lenalidomide or azacitidine was reduced due to dose limiting hematologic toxicity and continued treatment results in improvement of bone marrow function, dose increases by one dose level and drug at a time may be performed if the ANC is ≥ 1000 /mm³ and platelets are $\geq 50,000$ /mm³ at day one of the respective cycle if the previous cycle was completed without dose modifications due to toxicity (regardless of type). If patient's myeloma has previously been refractory to lenalidomide consideration should be given to increase azacitidine first, otherwise lenalidomide should be increased first. In general, drug dosing increases should alternate between lenalidomide and azacitidine until target doses of both drugs are reached or toxicity occurs but the treating physician may use clinical judgment and first increase one drug to target dose. After 12 months since initiation of protocol therapy, no further lenalidomide dose titration is permitted.

Dose Re-Escalation Upon Recovery of Kidney Function

If the patient's GFR increases from 30-59ml/min at enrollment to ≥ 60 ml/min at the start of a cycle and the previous cycle was tolerated without need for dose reduction of lenalidomide due to any adverse event and no G-CSF or platelet transfusions were required, the dose of lenalidomide may be increased by one dose level according to table 2. If the dose of lenalidomide or azacitidine was reduced due to renal impairment on study, and continued treatment results in calculated creatinine clearance ≥ 60 ml/min (by Cockcroft-Gault), the dose of lenalidomide and azacitidine can be increased by one dose level each at the start of each cycle until the target dose of both drugs is reached provided the calculated creatinine clearance remains ≥ 60 ml/min (by Cockcroft-Gault) and no relationship between study drugs and renal impairment was suspected. If a relationship between study drugs and renal impairment is considered possible, drug increases should be done one drug at a time and alternating between lenalidomide and azacitidine, starting with lenalidomide. Doses may be increased only in patients who completed the previous treatment cycle without dose modifications or treatment delays due to toxicity (regardless of type). Dose increases may occur NOT more frequently than once every 28 days. If the current dose of lenalidomide is 15 mg every 48 hours during Days 1-21 every 28 days, or 5 mg daily on Days 1-21 every 28 days, the first dose increase would be to 10 mg daily on Days 1-21 every 28 days. Additional dose increases if warranted would be in 5 mg increments. After 12 months since initiation of protocol therapy, no further lenalidomide dose titration is permitted.

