⁴: Dexamethasone dosing, independent of age, will be in the morning with breakfast. Dexamethasone should be taken at least 24h after and not less than 24h before azacitidine to maximize the s-phase specific epigenetic effects of azacitidine.

5.6.2.4 Lenalidomide Maintenance Treatment and Guidelines for Re-Introduction of Azacitidine and Dexamethasone

After six 28-day cycles on combination therapy, dexamethasone and azacitidine will be discontinued and lenalidomide will be continued as a single agent at the last tolerated dose until disease progression. At physician discretion, for patients with response < PR after six 28-day cycles on combination therapy, the dose of lenalidomide may be

escalated during maintenance treatment to a maximum dose of 25mg daily on Days 1-21 of each 28-day cycle. Lenalidomide dose titration may only occur at the start of a new cycle of maintenance one dose level at a time, and only in patients who completed the previous treatment cycle without dose modifications or treatment delays due to toxicity. Lenalidomide dose titration may occur NOT more frequently than once every 28 days. After 12 months since initiation of protocol therapy, no further lenalidomide dose titration is permitted. Also for patients with response < PR after six 28-day cycles on combination therapy, dexamethasone and/or azacitidine may be continued or restarted (if it had been discontinued) at physician discretion. In particular, patients with response < PR after six 28-day cycles on combination therapy that have not shown sufficient signs of end organ improvement should be considered for lenalidomide dose titration and/or additional dexamethasone and/or azacitidine as outlined above. Similarly, patients who have achieved disease control (stable disease or better) during the first six 28-day cycles of combination therapy and who's myeloma progresses on maintenance therapy may be restarted on lenalidomide, azacitidine, and dexamethasone combination therapy at the last tolerated dose at physician discretion.

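### Section 5.7.3 does not settle the lenalidomide step-up after renal recovery: a patient cut from 25 to 10 mg on study can be read as going next to 25 mg or to 15 mg

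*Combined protocol and SAP*

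**What the plan says.** The part of section 5.7.3 on recovery of kidney function is one paragraph with two entry conditions.

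- **Enrolled with reduced clearance.** The first rule opens "If the patient's GFR increases from 30-59ml/min at enrollment to" 60 ml/min or more at a cycle start. If the previous cycle was tolerated and needed no G-CSF or platelet transfusion, "the dose of lenalidomide may be increased by one dose level according to table 2".
- **Reduced on study.** The second rule opens "If the dose of lenalidomide or azacitidine was reduced due to renal impairment on study, and continued treatment results in calculated creatinine clearance" of 60 ml/min or more. It allows one level per drug at each cycle start until a target dose is reached. It names no table and does not define the target dose. From 15 mg every 48 hours or 5 mg daily, the first step is to 10 mg daily. Then: "Additional dose increases if warranted would be in 5 mg increments".

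Section 5.7.1.1 holds the two ladders, both written as reductions:

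- "Table 1: Lenalidomide dose modification steps for all toxicities listed in Table 5 EXCEPT for renal impairment or toxicities in the presence of renal impairment": 25, 20, 15, 10, 5 mg daily, stop.
- "Table 2: Lenalidomide dose modification steps for renal impairment (see Table 5) and for other toxicities which occur after dose reduction for renal impairment": 25 mg daily, 10 mg daily, 15 mg every 48 hours, 5 mg daily, stop.

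Table 5 sends a patient whose clearance falls to 30-59 ml/min on study to Table 2, and takes any dose of 15 mg or more down to 10 mg daily. The GFR 30-59 cohort starts at 10 mg daily (section 5.6.2.3).

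**The concern.** This is a dosing rule that staff at two sites apply at cycle starts, where clearance is checked every cycle until cycle 12. One paragraph uses two step sizes above 10 mg. The first rule points to a ladder with nothing between 10 and 25 mg daily. The second uses 5 mg steps that this ladder does not contain and that the other ladder offers only outside renal impairment.

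For the patient this is a safety matter: the same history can lead to different next-cycle doses, depending on which sentence is followed. For the analysis, section 10.2.2 reports toxicity by dose level up to cycle 12, and section 10.2.3 reports response after 6 and 12 cycles. The dose levels are labelled by azacitidine dose with lenalidomide fixed at the start. If re-escalation is read differently between sites or patients, later-cycle results under one label mix lenalidomide exposures that the plan did not intend to differ.

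**Working it through.** The plan gives no figure to reproduce, so the check is to apply each sentence to each kind of patient. All doses come from section 5.6.2.3, Tables 1 and 2, Table 5 and section 5.7.3.

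**1. Step up from 10 mg daily**

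- One level up Table 2: 25 mg daily.
- One 5 mg increment: 10 + 5 = 15 mg daily. This level is in Table 1 only.

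**2. Who meets which rule once clearance is 60 ml/min or more**

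- *Enrolled at 30-59, never reduced, on 10 mg.* Only the first rule applies. Next dose 25 mg. No conflict.
- *Enrolled at 60 or more, cut from 25 to 10 mg under Tables 5 and 2.* Only the second rule applies. It permits one level with no table named. Reversing the Table 2 step gives 25 mg; the increment sentence gives 15 mg. Both readings are open.
- *Enrolled at 30-59, reduced on study for renal impairment, brought back to 10 mg.* The first rule gives 25 mg. Whether the second also applies depends on the target dose. If that is the assigned 10 mg, the second rule has ended and only 25 mg remains. If it is 25 mg, the second rule also applies and gives 15 mg.

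**3. Size of the difference**

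Lenalidomide per cycle = daily dose × 21 days.

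- At 10 mg: 10 × 21 = 210 mg.
- After a Table 2 step: 25 × 21 = 525 mg, and 525 / 210 = 2.5.
- After a 5 mg step: 15 × 21 = 315 mg, and 315 / 210 = 1.5.
- Ratio of the two readings: 525 / 315 = 1.67. The higher dose is 67% above the lower, or 525 - 315 = 210 mg more per cycle.

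Section 5.1.1.3 states that lenalidomide concentrations are dose proportional from 5 to 50 mg, so at a given clearance the ratio carries over to exposure.

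**4. How long the difference lasts**

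Table 2 reaches 25 mg in one step. Increments need (25 - 10) / 5 = 3 steps, at most one every 28 days. If every increase is taken at consecutive cycle starts, the three cycles give 315 + 420 + 525 = 1,260 mg by increments and 3 × 525 = 1,575 mg by Table 2, a ratio of 1.25. The gap is largest in the first cycle after recovery and closes in the third. Skipped or refused increases would make it last longer.

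**5. What it can reach**

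DLT is counted in the first 28-day cycle (section 5.1). Both rules act at the start of a later cycle, so the earliest effect is in cycle 2.

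**The case against.** **The triggers differ, perhaps by design.** This stands in part. A reader might infer that any two patients on 10 mg with clearance of 60 or more face conflicting instructions. The text does not support that: a never-reduced patient enrolled at 30-59 has one literal step, and treating different renal histories differently may be intended. The conflict lies within the on-study rule and in the overlap of the two rules.

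**The increment sentence may cover only patients who first climbed from 15 mg every 48 hours or 5 mg daily.** It does follow those cases, and the word *additional* can be read that way. A patient cut straight from 25 to 10 mg would then be left with one level and no table. That is still unresolved.

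**A recovered patient no longer has renal impairment as the table footnotes define it, so Table 1 may be used.** That supports the 15 mg reading. But the first rule sends an equally recovered patient to Table 2, so the definition does not settle the matter.

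**The foot of the ladder.** A reader might see a second conflict there, because one Table 2 level above 5 mg daily is 15 mg every 48 hours. Section 5.7.3 expressly gives 10 mg daily as the first step from either dose, and a specific instruction governs over a general one.

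**The consequence is limited.** This stands. Increases are optional and require a tolerated previous cycle. Both candidate doses appear among the protocol's own dose levels. Later-cycle exposure already varies through toxicity reductions and azacitidine escalation.

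**Conclusion.** The inconsistency is real and should be corrected. For a patient cut from 25 to 10 mg on study who then recovers, the protocol supports a next dose of 25 mg or 15 mg: 525 versus 315 mg per cycle, ratio 1.67. For a patient enrolled at 30-59, reduced on study and brought back to 10 mg, the same split arises only if the target dose is above 10 mg, which the protocol does not say.

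The ratio rests on 21 dosing days and the stated dose steps, with no outside assumption. No view is taken here on which step is right.

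Three stronger readings are not supported:

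- That dose selection is compromised. HTLD and HTLD-CKD rest on first-cycle DLT, before either rule can act.
- That all later results of the GFR 30-59 cohort lack a governing lenalidomide rule. Its never-reduced patients have one.
- That a frequency can be attached. The documents give neither the distribution of clearance at entry nor its variation within a patient, and the chance of crossing 60 ml/min is not the chance that the two sentences collide.

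What is affected is later-cycle lenalidomide exposure and, through it, safety by dose level and response.

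**What to change.** Reconcile the sentences of section 5.7.3 with Tables 1 and 2. For each of three groups (GFR 30-59 at enrolment; reduced on study for renal impairment; both), state which ladder applies upward and what the target dose is. The clinical team must decide the steps, and whether the groups should differ.

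Add a cross-reference in section 5.6.2.4. Its maintenance rule, "Lenalidomide dose titration may only occur at the start of a new cycle of maintenance one dose level at a time", is driven by response rather than renal recovery and is a separate matter, but it also names no ladder.

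In the later-cycle safety and response summaries, show how many patients had left their assigned lenalidomide dose, and in which cycle.

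The cost is a few sentences in an amendment and one extra line in the exposure table. No patients or procedures are added.
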